4.15.3. Analyses of Erectile Dysfunction

Another additional objective is to evaluate the effect of dulaglutide compared to placebo on the IIEF scores in men. This objective will be assessed using the measure of change from baseline to each visit in total IIEF scores from the 15-item questionnaire in the erectile function (EF), orgasmic function, sexual desire, overall satisfaction (OS), and intercourse satisfaction (IS) domains. The analysis will use an MMRM model that includes among others (Section 4.3.2) terms for treatment and the baselines values minus their mean as covariate. The population for these analyses will be all randomized male patients.

4.15.4. Analyses of Other Additional Measures

Time-to-event analyses will be performed for each of the following endpoints: the composite endpoint of death from CV causes, non-fatal MI, nonfatal stroke, or hospitalization for unstable angina; the composite endpoint of coronary, carotid, or peripheral revascularization and each of the components; any hospitalization; any fracture; and the development of cholelithiasis. A Cox proportional hazards regression model for the time to the first occurrence of the event, with treatment as fixed effects will be performed for the ITT population. Kaplan-Meier curves, hazard ratios and associated 95% CIs will be provided. Treatment groups will be compared using the p-value from the Cox model. The population for the analysis of cholelithiasis will be all randomized patients who have not had a cholecystectomy before randomization.

Revascularizations are classified as elective or nonelective and as successful or not successful. The number and proportion of revascularizations falling in each category will be compared between treatment groups using a Chi-square or Fisher's exact tests. Reasons for hospitalization (adverse Event, endpoint, or other) will also be compared between treatment groups.

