4.3. Default Analysis Methods

A default analysis method will be defined for certain types of variables (for example, baseline continuous, baseline categorical and time-to-event) that will be commonly encountered in this study. If a specific analysis requires a methodology other than the default for that variable type, the methodology will be described in the appropriate sections of this SAP.

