4.3.3. Post-baseline Analyses of Categorical Variables

Categorical variables will be compared between treatment groups using the Pearson chi-square test if the expected count is at least 5 in at least 80% of the cells; otherwise, Fisher's exact test will be used. Summaries for these variables will include the between-treatment p-value and the

descriptive statistics: number and proportion of patients. For post-baseline outcome variables, the relative risk estimate and the associated 95% CI will be provided, if there are at least 10 patients with the outcome.

If the categorical variable is associated with a scheduled post-baseline measurement, then a patient must have a measurement of the variable to be included. However, when the categorical variable is the occurrence of an event (yes/no), such as development of an adverse event (AE), then all randomized patients will be included in the analysis.

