4.14.2.1.2. Other Classifications of Myocardial Infarction

The adjudicators will also classify MI type as STEMI vs NSTEMI and by subtypes of MI (Spontaneous, Periprocedural [PCI or CABG related], or Silent). Myocardial infarction types will be summarized using number and proportion of patients for both treatment groups using these different classification schemes. For these analyses, the denominator will be the total number of patients having an MI. If a patient has >1 MI, only the first MI will be included in the analysis.

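### SAP 4.15.4 compares elective/nonelective and successful/unsuccessful revascularizations by chi-square with the procedure as the unit, so repeat procedures in one patient are treated as independent (minor)

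*SAP*

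**What the plan says.** SAP 4.15.4 plans two kinds of analysis for revascularization. The first is a Cox model for time to first event, for the coronary, carotid or peripheral composite and for each component. That counts each patient once and is not in question.

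The second is a breakdown by type of procedure: "Revascularizations are classified as elective or nonelective and as successful or not successful". The comparison is then defined: "The number and proportion of revascularizations falling in each category will be compared between treatment groups using a Chi-square" or Fisher's exact test. The section does not say how a patient with several procedures enters the table.

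Elsewhere the SAP counts patients:

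- SAP 4.3.3, the default for post-baseline categorical variables, specifies "descriptive statistics: number and proportion of patients".
- SAP 4.14.2.1.2, the closest parallel (MI by type), uses patients with an MI as the denominator and adds: "If a patient has >1 MI, only the first MI will be included in the analysis".
- SAP 4.3 explains how section text relates to the defaults: "If a specific analysis requires a methodology other than the default for that variable type, the methodology will be described" in the section concerned.

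**The concern.** Pearson's chi-square and Fisher's exact test both need independent observations. Average follow-up is planned at about 6.5 years (Protocol Synopsis), and the table spans three vascular beds, so some patients can be expected to have more than one procedure. If a patient's procedures resemble each other in urgency or outcome, the effective sample size is smaller than the number of procedures. The test's standard error is then too small, and it will declare a difference between arms more often than its nominal rate.

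What is at stake is the credibility of one supporting p-value on whether dulaglutide changes the mix or success of procedures. SAP 4.2 sets a 2-sided 0.05 level for tests of treatment effects, and SAP 4.3.6.1 makes no multiplicity adjustment for endpoints outside its graph. Nothing else holds the error rate of this comparison to its stated level.

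**Working it through.** **Does another section repair the wording?**

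| Place | What it covers | Does it settle the unit in this table? |
|---|---|---|
| SAP 4.3.3 | Patient-level default | No. SAP 4.3 lets a section's own method replace the default, and 4.15.4 names revascularizations |
| SAP 4.3.4.1 | First event used when there are several | No. It defines time to event |
| SAP 4.14.2.1.2 | First MI only | No. MI only |
| SAP 4.14.6 | Recurrent-event model | No. Revascularization is not among its endpoints |
| Protocol 12.2.10 | Cox model for revascularization | No. It has no such table |

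Followed as written, 4.15.4 therefore uses the procedure as the unit.

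**How large is the effect?** The documents state no figure for this comparison, so there is nothing to reproduce. Only the nominal level (0.05, 2-sided, SAP 4.2) and the 1:1 allocation (SAP 4.4) come from the documents. The number of procedures per patient, m, and the within-patient correlation of category, rho, are assumptions.

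Design effect: D = 1 + (Σm²/Σm − 1) × rho.

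Actual type I error of the unadjusted test: α = 2 × [1 − Φ(1.96/√D)].

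For a geometric count with mean μ, Σm²/Σm = 2μ − 1, so D = 1 + (2μ − 2) × rho.

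| Mean procedures | rho | D | 1.96/√D | α |
|---|---|---|---|---|
| 1.2 | 0.2 | 1 + 0.4 × 0.2 = 1.08 | 1.886 | 5.9% |
| 1.2 | 0.5 | 1 + 0.4 × 0.5 = 1.20 | 1.789 | 7.4% |
| 1.4 | 0.5 | 1 + 0.8 × 0.5 = 1.40 | 1.656 | 9.8% |
| 1.6 | 0.5 | 1 + 1.2 × 0.5 = 1.60 | 1.550 | 12.1% |

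**Sensitivity to the count distribution.** The same formula with fixed distributions of one to four procedures gives:

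| Revascularized patients with repeats | Mean | Σm²/Σm | α, rho 0 | α, rho 0.2 | α, rho 0.5 | α, rho 1 |
|---|---|---|---|---|---|---|
| 10% | 1.14 | 1.333 | 5.0% | 5.8% | 7.0% | 9.0% |
| 20% | 1.29 | 1.620 | 5.0% | 6.5% | 8.7% | 12.4% |
| 35% | 1.55 | 2.032 | 5.0% | 7.4% | 11.1% | 16.9% |

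**Negative correlation.** With 35% repeats and rho −0.1, D = 1 − 1.032 × 0.1 = 0.897 and α is about 3.9%, so the test is conservative.

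**Simulation check.** A beta-binomial simulation under the null used the three distributions in the second table (assumed 400 revascularized patients per arm, category probability 0.5, 8000 runs per setting). It agreed with the formula to within about one percentage point. With one record per patient, type I error was 5.0% to 5.3% in every setting. A second simulation with geometric counts and 350 revascularized patients per arm gave 7.5%, 9.4% and 12.0% at rho 0.5 for means 1.2, 1.4 and 1.6. A patient-clustered variance brought these to between 4.9% and 5.3%.

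**The case against.** **The direction is not documented.** This stands. The p-values are too small only if category is positively correlated within patient. Staged care could pull the other way: a nonelective index procedure may be followed by an elective one, or a failed attempt by a successful one. A reader might infer that the test is anticonservative as a matter of fact. The documents support only the conditional statement.

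**The effect may be close to nil.** This also stands. With few repeats and low correlation, α is 5.8% to 5.9%.

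**The consequence is small.** This stands and sets the severity. The table is an unadjusted breakdown of an additional measure. A reader might infer that the plan's revascularization results in general are compromised. They are not: coronary, carotid and peripheral revascularization are each analysed by time to first event.

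**The wording may be loose and the default may apply.** This does not stand. SAP 4.3 gives precedence to the method described in the section, and 4.15.4 names the procedure as the counted unit.

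**The next sentence may have the same fault.** It reads: "Reasons for hospitalization (adverse Event, endpoint, or other) will also be compared between treatment groups". A reader might infer that admissions are the unit there too. The sentence names neither a unit nor a test, so the patient-level default in SAP 4.3.3 applies. The documents do not support extending the point to hospitalizations.

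**Conclusion.** The point holds, as a minor one. As written, the elective/nonelective and successful/unsuccessful comparison in SAP 4.15.4 treats repeat procedures in a patient as independent, and no other section corrects it. Whenever repeats occur and their categories are correlated within patient, the stated tests use the wrong variance.

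Under positive correlation of 0.2 to 0.5 and means of 1.2 to 1.6 procedures per revascularized patient, the nominal 5% becomes about 5.9% to 12.1%. Those inputs are assumptions, because the documents give neither repeat frequency nor correlation. The fault lies in the test's variance and is confined to this one table.

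**What to change.** In SAP 4.15.4, classify each patient by the first revascularization after randomization. Use patients with a revascularization as the denominator, and compare arms by chi-square or Fisher's exact test. This matches what SAP 4.14.2.1.2 does for MI and keeps the question the section asks, which is the mix of procedures.

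If all procedures are to be kept, report the procedure-level proportions and take the p-value and confidence interval from a patient-clustered method, such as GEE with robust variance or a Rao-Scott chi-square.

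Counting randomized patients with at least one procedure in each category is a less suitable substitute. It measures incidence rather than mix, and one patient can fall in both categories.

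The cost is one SAP sentence and a small programming change. No new data are needed.

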4.16. Other Exploratory Analyses

4.16.1. Analyses of Time to Glycemic Intervention

Additional therapeutic intervention may be considered (with the exception of a GLP-1 analog or pramlintide) in patients who do not attain target HbA1c values and/or develop severe hyperglycemia, despite full compliance with the assigned study treatment regimen. These changes may be instituted 3 months after randomization to enable the effects of study drug on HbA1c to stabilize, unless sooner intervention is indicated, in the judgment of the investigator.

According to the protocol, patients should continue to inject their allocated study drug and will remain in the study.

Time-to-event analyses will be performed for the time to the first glycemic intervention after randomization. The incidence of glycemic interventions will be summarized using number and proportion of patients by treatment group and by visit. The overall number and proportion will also be reported as will, Kaplan-Meier estimates of the proportion of patients having 1 or more glycemic intervention by treatment group. The number and proportion at each visit are calculated as the number of patients and proportion of patients reporting glycemic interventions at that visit. The overall number and proportion are calculated as the total number of patients and proportion of patients reporting severe glycemic interventions during the entire study treatment period. Treatment group comparison will be assessed using a Chi-square or Fisher's exact tests or log-rank tests as appropriate. The mean time to initiation of additional therapies will be compared between treatment group using an ANOVA model with treatment and additional covariates such as baseline HbA1c and concomitant antihyperglycemic agents.

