4.3.4. Time-to-Event Analyses

Time-to-event analyses will be performed for each of the adjudicated outcomes. For each analysis, all adjudicated events in the locked database will be used.

Time-to-event variables will be analyzed using survival analysis methodology if the total number of outcomes is 10 or more. A Cox proportional hazards regression analysis, where the model only includes a fixed effect for treatment, will be used to derive the hazard ratio (dulaglutide/placebo) and the associated 95% CI. The between-treatment comparison will be based on the p-value from the Cox model. The proportional hazard assumption will be examined graphically. If not met, data will be analyzed using accelerated failure time models. Kaplan-Meier (KM) estimates of the survival curve for each treatment will be generated. The number and proportion of patients with the event will be provided, along with the between-treatment p-value. Tied event times will be handled by the Exact method.

If the number of outcomes is <10, survival analyses will not be performed. Instead, Fisher's exact test will be used and the summary statistics will include the number and proportion of patients with the event plus the between-treatment p-value.

For adjudicated outcomes, the incidence rate per 100 person-years of follow-up will be calculated for each treatment group. The numerator will be the number of patients with the event, and the denominator will be the event-specific total person-years of follow-up divided by 100. Total person-years of follow-up is the sum, over patients, of the time on study until the first outcome (first event time or censoring time). The absolute risk difference (ARD) will then be calculated by subtracting the incidence in the dulaglutide arm from that in the placebo arm. For some analyses, the number needed to treat (NNT) to prevent an additional event will be derived using the incidence rates, that is, $1/(\text{Placebo rate} - \text{dulaglutide rate})$. These analyses will be performed where documented in the SAP, and this statistic will only be derived if the p-value from the Cox model is statistically significant.

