4.3.4.3. Censoring Date

For time-to-event analyses (except for mortality analyses), the censoring date for a patient is the Final Visit date if a Final Visit was conducted, the discontinuation date if the patient discontinues from the study early, or the patient's date of death if the patient dies during the course of the study. This censoring date will be used in all analyses (except the mortality analyses) to censor patients who have not experienced the event of interest.

For time-to-event analyses for mortality, the censoring date for a patient is the Final Visit date if the patient is known to be alive at the time of the Final Visit. If the patient discontinues from the study early, the censoring date will be the last date that the investigator can ascertain the patient was alive.

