If any of the 3 hypotheses above are rejected, the graph is again updated and its alpha is reallocated to the subsequent tests according to the weights given in the figure. It should be noted it is possible for the hypothesis for a particular endpoint to fail to be rejected the first time it is tested, but subsequently receive enough α from successfully rejected hypotheses and be rejected the second time it is tested. This iterative process of updating the graph and redistribution of α is continued until no further hypotheses can be tested.

The graphical approach to multiplicity control has been evaluated in several peer reviewed publications: Bretz and colleagues (2009), Bretz and colleagues (2011); and Alosch and colleagues (2014). Because graphical approaches are closed testing procedures, they control the FWER strongly (Alosch et al. 2014). This closed testing system controls the FWER to ≤ 0.05 .

Abbreviations: A-C Mortality = all-cause mortality; CV = cardiovascular; HUA = hospitalization for unstable angina; MACE = major adverse cardiovascular event; MI = myocardial infarction.

Figure GBDJ.4.2. The graphical approach with initial α allocation and weights at the final analysis time point with 1200 primary MACE events.

Abbreviations: A-C Mortality = all-cause mortality; CV = cardiovascular; HUA = hospitalization for unstable angina; MACE = major adverse cardiovascular event; MI = myocardial infarction.

Figure GBDJ.4.3. The graphical approach reflecting α propagation after rejecting the first hypothesis at the final analysis time point with 1200 primary MACE events.

No adjustments will be made for multiple comparisons on other endpoints.

4.3.6.2. Interim Analysis and Control of Type I Error following an Efficacy Stop Decision

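### The exploratory ANOVA on mean time to added glucose-lowering therapy (SAP 4.16.1) cannot handle patients who never start one and should be replaced by methods that respect censoring

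*SAP*

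**What the plan says.** SAP 4.16.1 stands under the heading "4.16. Other Exploratory Analyses". It first states: "Time-to-event analyses will be performed for the time to the first glycemic intervention after randomization". It adds incidence by visit and overall, Kaplan-Meier proportions, and this: "Treatment group comparison will be assessed using a Chi-square or Fisher's exact tests or log-rank tests as appropriate". The last sentence of the section then introduces a further method: "The mean time to initiation of additional therapies will be compared between treatment group using an ANOVA model". That model carries treatment and further covariates, of which HbA1c at baseline and other glucose-lowering drugs are given as examples.

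Three other places bear on it.
- SAP 4.3.4.3 sets a censoring date for time-to-event analyses: "This censoring date will be used in all analyses (except the mortality analyses) to censor patients who have not experienced the event of interest".
- SAP 4.3.4 defines the default model: "A Cox proportional hazards regression analysis, where the model only includes a fixed effect for treatment".
- SAP 4.3.6.1 places this endpoint outside the testing graph: "No adjustments will be made for multiple comparisons on other endpoints".

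Neither document names the population for the ANOVA or the value given to a patient who never starts an additional therapy.

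**The concern.** An ANOVA needs a number for every patient it includes. A patient followed to the end without intensification supplies only a lower bound. The censoring rule in 4.3.4.3 does not rescue the analysis: it provides a date, but an ANOVA has no way to mark that date as censored. Two readings are left.

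- **Initiators only.** Each arm's mean is taken over patients selected by an event after randomization. A glucose-lowering drug is expected to change who those patients are, so the comparison is no longer the randomized one.
- **Censoring time entered as if it were the event time.** All patients stay in, but the result mixes time to initiation with length of follow-up and is not a mean time to initiation.

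At stake is an ANOVA estimate and p-value printed beside the log-rank result for the same endpoint, and possibly disagreeing with it. Because the default Cox model contains treatment only, the ANOVA is also the only covariate-adjusted comparison that 4.16.1 names. Its covariate for concomitant agents is not restricted to baseline, so as worded it could include the added therapies that define the outcome.

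**Working it through.** **Plan's own figure.** None. The documents give no intervention rate, effect size or power for this analysis, so all rates below are assumptions.

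**Inputs from the documents.** Average follow-up of about 6.5 y, minimum 5.6 y, and about 9600 patients randomized 1:1, hence 4800 per arm (Protocol 7.1). Enrollment took 2.1 y (Protocol Attachment 5), so censoring is spread over 5.6 to 5.6 + 2.1 = 7.7 y. Dropout is 0.15% per year (SAP 4.1). Deaths are not modelled.

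**Formulas.** With follow-up τ, hazard h and proportion intensified p = 1 − exp(−hτ):
- restricted mean time free of added therapy (RMST) = p/h
- mean among initiators = (RMST − τ(1 − p))/p = 1/h − τ(1 − p)/p

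**Step 1: how many have no event time.** With censoring uniform on 5.6 to 7.7 y and the stated dropout, the share of placebo patients who never initiate is 82%, 72%, 52%, 27% and 14% at assumed hazards of 0.03, 0.05, 0.10, 0.20 and 0.30 per year.

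**Step 2: proportional hazards, τ = 6.5 y, 60% (placebo) against 40% (drug) intensified.**
- Placebo: h = −ln(0.4)/6.5 = 0.1410. RMST = 0.6/0.1410 = 4.26 y. Initiator mean = 7.09 − 6.5 × 0.4/0.6 = 2.76 y.
- Drug: h = −ln(0.6)/6.5 = 0.0786. RMST = 0.4/0.0786 = 5.09 y. Initiator mean = 12.72 − 6.5 × 0.6/0.4 = 2.97 y.
- Difference: +0.21 y among initiators, +0.83 y in RMST.

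The same formulas give +0.26 against +0.91 y at 70%/50%, and +0.14 against +0.59 y at 50%/35%.

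**Step 3: proportional hazards with the trial's censoring spread, placebo hazard 0.10, HR 0.75.** 48.3% (placebo) and 39.0% (drug) initiate. Initiator means are 2.97 and 3.06 y: +0.09 y, expected z about 1.6 at 4800 per arm. RMST to 5.6 y is (1 − e^−0.56)/0.10 = 4.29 y against (1 − e^−0.42)/0.075 = 4.57 y, or +0.28 y.

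**Step 4: when direction can reverse.** The ratio of the event-time densities, drug to placebo, is HR(t) × S_drug(t)/S_placebo(t). With HR below 1 and constant or rising over time, this ratio increases with t. With equal censoring the initiator mean on drug is then the later one, so there is no reversal in expectation. Reversal needs an HR that falls over time, meaning a stronger effect on later interventions. Three examples:
- No effect in year 1, then a lower hazard, ending at 62% against 38% by 6.5 y. Placebo h = −ln(0.38)/6.5 = 0.1489. Drug hazard after year 1 = (−ln(0.62) − 0.1489)/5.5 = 0.0599, an HR of 0.40. Drug RMST = (1 − 0.8617)/0.1489 + (0.8617 − 0.62)/0.0599 = 0.93 + 4.04 = 4.97 y, against 0.62/0.1489 = 4.17 y. Initiator means: drug (4.97 − 6.5 × 0.62)/0.38 = 2.47 y, placebo 2.73 y. This is reversed.
- Placebo hazard 0.10, HR 0.9 to year 2 then 0.5, trial censoring: initiators −0.31 y (z −5.0), RMST to 5.6 y +0.29 y.
- 20% fast failures (hazard 1.0/y) unaffected, the rest at hazard 0.05 with HR 0.6: initiators −0.21 y (z −3.4), RMST +0.22 y.

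**Step 5: censoring times used as event times.** No scenario reversed; differences ranged from +0.06 to +0.99 y. The second and third examples of Step 4 give +0.44 and +0.30 y.

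**The case against.** The strongest reply is about weight. The endpoint is not among the primary, secondary, safety or additional objectives, no alpha or stopping rule depends on it, and the same paragraph already plans analyses that handle censoring. All of that stands, and it makes this a limited point.

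The second reply concerns reversal. A reader might infer that the ANOVA will make the drug look worse. The documents do not support that: they give no rates and do not say that only initiators are analysed. SAP 4.16.1 itself allows about 3 months for HbA1c effects to stabilize. If the no-effect period in the first example of Step 4 ends at 3 months, the initiator means are 2.73 y (placebo) against 2.85, 2.84 and 2.80 y (drug) for later HRs of 0.4, 0.6 and 0.8, with no reversal. Keeping the full-year delay, the differences are −0.27, −0.10 and −0.02 y for the same HRs. Reversal is therefore a possibility under particular assumptions.

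Third, a reader might take an adjusted Cox model as already planned. It is not. The default in 4.3.4 has treatment only, and for the clinical study report 4.3.1 admits a baseline covariate only if it differs both clinically and statistically between groups.

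Finally, the mean could be kept as a description of initiators without a p-value. That would remove the misleading test, but it would leave the section without a valid adjusted comparison.

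None of this defends the ANOVA itself. Both ways of carrying it out fail to estimate what the sentence names.

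**Conclusion.** The point holds as a defect of method in one exploratory analysis. It is more than missing detail, because choosing either reading would not make the ANOVA valid. Under proportional hazards and equal censoring, the initiators-only mean keeps its direction but shrinks, to about a quarter of the restricted-mean gain in the 60%/40% example (0.21/0.83). A wrong sign requires that reading plus an effect concentrated on later interventions. Every magnitude rests on assumed hazards and hazard ratios and ignores deaths.

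A reader should not infer that a trial conclusion or the type I error rate is at risk, or that the endpoint lacks a valid analysis. The practical consequence is a possibly contradictory p-value, and an adjusted comparison that exists only in invalid form.

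**What to change.** In SAP 4.16.1:

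1. Delete the ANOVA sentence.
2. If a mean time is wanted, report the difference in restricted mean time free of added therapy to a common horizon within minimum follow-up, for example 5 years (the projected minimum is 5.6 y).
3. For the adjusted comparison, add a Cox model with treatment, baseline HbA1c and baseline glucose-lowering drugs, excluding agents started after randomization. Write it as an explicit addition to the treatment-only default in 4.3.4 and as an exception to the covariate rule in 4.3.1.
4. State that death before intensification is handled as in 4.3.4.3, that is, censored at the date of death.

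The cost is minor SAP wording and programming. The data are the same, and no primary or alpha-controlled analysis changes.
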